8.1.1 Clinical Laboratory Analyses

All clinical laboratory values will be listed individually and tabulated in a manner to identify safety concerns on a per-patient basis. Listing tables will be prepared for each laboratory measure and will be structured to permit review of the patient data as they progress on treatment. The tables will list the cycle of treatment, copanlisib and fulvestrant doses for dose confirmation data, and the associated NCI CTCAE grade. Descriptive summary statistics will be generated per laboratory parameter.

Summary tables will be prepared to examine the distribution of these toxicities per cycle.

Proprietary Information of MD Anderson

Protocol 2020-1241

19 October 2022

Graphic displays and shift tables may be provided to illustrate results over time on study. Assessment of cumulative toxicities may be made.

8.2 Efficacy Analysis

The ORR is defined as the proportion of patients who achieve CR or PR by the combination therapy per RECIST 1.1. Bayesian beta-binomial model and the CBHM will be used to model the data observed within each cohort. Bayesian 95% credible interval will be derived. Summary statistics will be given for secondary efficacy endpoints without borrowing information across cohorts. Time-to-event methodology will be used to assess mortality outcomes. Specifically, a log-rank statistic (accompanied by a Kaplan-Meier plot) will be the primary method of analysis for the mortality endpoint. Model-based methods (e.g., Cox proportional hazards or other robust methods) may also be applied.

8.3 Data Collection

8.3.1 Data Protection and Confidentiality

All patients who meet eligibility criteria and are enrolled in this study will be registered in Clinical Oncology Research e-Database (CORE) at MDACC. All study patients must be registered in the CORe. The date of the current ICF is displayed to ensure only the most current IRB-approved version is used. Consent date, registration date, off study date, and evaluability data are required for all registrants.

The investigator agrees to keep all information and results concerning the study confidential. The confidentiality obligation applies to all personnel involved with this clinical study. The investigator must ensure that each study patient's anonymity will be maintained in accordance with applicable laws. The investigator should keep a separate log of identification numbers, names, and addresses. Documents that contain the names associated with these identification numbers (e.g., written consent/assent forms) should be maintained by the investigator in strict confidence except to the extent necessary to allow auditing by regulatory authorities, auditing or monitoring by the IRB.

The investigator shall obtain all such permissions and authorizations as may be necessary or desirable to allow the collection and use of information protected under federal privacy laws and state privacy laws, including permission/authorization for monitoring and analysis (including re-analysis in combination with results of other studies), for regulatory submission purposes and applicable reporting (if any).

Protocol-specific data will be entered into MOCLIP/CORe (or other databases); MOCLIP/CORe (or other databases) will be used as the eCRF.

Proprietary Information of MD Anderson

Protocol 2020-1241

19 October 2022

9 Ethical and regulatory requirements

This study will be conducted in full conformance with the ICH E6 guideline for GCP and the principles of the Declaration of Helsinki. The study will comply with United States FDA regulations and applicable local, state, and federal laws. Details are described in the MD Anderson institutional standard operating procedures and policies.

APPENDIX A: SCHEDULE OF ASSESSMENTS

Study Period	Screening/ Baseline	(EOT)/ Progression ^a									Post-Treatment				
Treatment Cycle/ Title		Cycle 1 (28 days)			Cycle 2 (28 days)			Subsequent cycles (28 days)				Safety follow-up visit ^b	Follow-up Visits	Survival Follow-up	
Day of cycle		1 ^c	8	15	22	1	8	15	1	8	15	≤28 days from the last dose	30 days post last dose	Every 8 weeks	Every 12 weeks
Scheduling window	Days -28 to -1	±2 days	±2 days	±2 days	±2 days	±2 days	±2 days	±2 days	±2 days	±2 days	±2 days	±5 days	±5 days	±7 days	±14 days
Informed consent	X														
PI3K pathway and PTEN status	X														
Hormone receptor expression status	X														
CMV, HBV and HCV testing ^d	X														
Demographics and Medical History	X														
Adverse event assessment ^e	X	CONTINUOUS													
Inclusion/exclusion criteria	X														
Cancer treatment history	X														
Prior/concomitant medications ^f	X	CONTINUOUS													
Archival tumor collection ^g	X														
Imaging and other															
CT/MRI	X								X ^h			X ^h		X ⁱ	

Study Period	Screening/ Baseline	(EOT)/ Progression ^a									Post-Treatment				
Treatment Cycle/ Title		Cycle 1			Cycle 2			Subsequent cycles				Safety follow-up visit ^b	Follow-up Visits	Survival Follow-up	
Day of cycle		1 ^c	8	15	22	1	8	15	1	8	15	≤28 days from the last dose	30 days post last dose	Every 8 weeks	Every 12 weeks
Scheduling window	Days -28 to -1	±2 days	±2 days	±2 days	±2 days	±2 days	±2 days	±2 days	±2 days	±2 days	±2 days	±5 days	±5 days	±7 days	±14 days
Tumor assessment	X								X ^h			X ^h		X ⁱ	
Study drug administration															
Copanlisib administration ^j		X	X	X		X	X	X	X	X	X				
Fulvestrant administration ^k		X		X		X		X							
Clinical Procedures															
Physical examination ^l	X	X	X	X	X	X		X	X			X			
ECOG performance status ^l	X	X	X	X	X	X		X	X			X			
Vital signs (BP ^m , HR, body temperature, RR, O ₂ saturation) ^l	X	X	X	X	X	X		X	X			X			
Height	X														
Weight	X	X	X	X	X	X		X	X			X			
MUGA scan/ ECHO ⁿ	X														
Single 12 lead ECG	X	X				X			X						
Clinical laboratory tests															
Hematology (CBC plus differential) ^o	X	X	X	X	X	X		X	X			X			
Clinical chemistry ^p	X	X	X	X	X	X		X	X			X			
Urinalysis	X	X				X			X			X			

Study Period	Screening/ Baseline	Treatment									(EOT)/ Progression ^a	Post-Treatment			
Treatment Cycle/ Title		Cycle 1				Cycle 2			Subsequent cycles				Safety follow-up visit ^b	Follow-up Visits	Survival Follow-up
Day of cycle		1 ^c	8	15	22	1	8	15	1	8	15	≤28 days from the last dose	30 days post last dose	Every 8 weeks	Every 12 weeks
Scheduling window	Days -28 to -1	±2 days	±2 days	±2 days	±2 days	±2 days	±2 days	±2 days	±2 days	±2 days	±2 days	±5 days	±5 days	±7 days	±14 days
Blood collection for ctDNA ^q	X					X			X ^q			X			
Tumor biopsies ^r	X					X						X			
Pregnancy test	X ^s	X ^{t,u}				X ^t			X ^t						
FPG ^v	X	X	X	X		X	X	X	X	X	X				
Survival Status ^w															X

AE = adverse event; ALP = alkaline phosphatase; ALT = alanine transaminase; AST = aspartate transaminase; BP = blood pressure; CBC = complete blood count; CMV = cytomegalovirus; ctDNA = circulating tumor DNA; CT = computed tomography; ECG = electrocardiogram; ECHO = echocardiogram; ECOG = Eastern Cooperative Oncology Group; EOT = end of treatment; FPG = fasting plasma glucose; h = hour(s); HBV = hepatitis B virus; HbsAg = HBV surface antigen; HbcAb = HBV core antibody; HCV = hepatitis C virus; HR = heart rate; IM = intramuscular; IV = intravenous; min = minute(s); MRI = magnetic resonance imaging; MUGA = multigated acquisition; O2 = oxygen; PCR = polymerase chain reaction; RR = respiratory rate; TB = Total bilirubin; WBC = white blood cell.

- a) After discontinuation of study drugs, patients will complete an EOT visit within 28 days after the last study drug dose.
- b) A safety follow-up visit is to be conducted 30 days (±7 days) after the last dose of study drug and later if drug-related AEs have not resolved at that time. After that, patients without documented disease progression will be followed every 8 weeks for disease assessments until documentation of disease progression. After documentation of disease progression, patients will be followed every 12 weeks for survival status; such follow-up will likely be conducted by telephone.
- c) If Cycle 1 Day 1 occurs <72 hours after Screening, physical examinations, and clinical laboratory tests do not need to be repeated.
- d) Patients will be excluded if they are positive for CMV or active HBV or HCV infection requiring treatment. CMV will be tested by PCR at screening. Active HBV (chronic or acute) is defined as having a known positive HbsAg at the time of screening. Participants with past HBV infection or resolved infection (defined as the presence of HbcAb and absence of HbsAg) are eligible if HBV DNA is negative. Participants with positive HCV antibody are eligible only if PCR is negative for HCV RNA.
- e) AEs will be captured from the time of informed consent signing through 30 days after the last dose of study drug or initiation of a new anticancer therapy, whichever comes first.

- f) All concomitant medication received within 28 days prior to study drug initiation and 30 days after the last dose of study drug will be recorded, including all prescription, over-the-counter, IV medications and fluids, supportive care drugs and the drugs used to treat AEs or chronic diseases, and non-drug supportive interventions. If changes occur during the study period, documentation of drug dosage, frequency, route, and date will also be recorded.
- g) Archival tissue will be collected if available.
- h) Radiographic tumor assessments, using CT scanning or MRI, will be performed at Screening, Cycle 3 Day 1 (± 7 days), Day 1 (± 7 days) of every 2nd cycle after that, and at EOT.
- i) Patients who discontinue study treatment for a reason other than disease progression will move into follow-up phase. Patients will be monitored for disease status by tumor imaging (CT scan or MRI, as appropriate) every 8 weeks (± 7 days) until PD, death, initiation of new anticancer therapy, withdrawal of consent, or lost to follow-up.
- j) Copanlisib (60 mg IV) will be administered on Day 1, Day 8, and Day 15 of 28-day cycles until disease progression, unacceptable toxicity, death, withdrawal of consent, or discontinuation from the study drug for any other reason.
- k) Fulvestrant (500 mg IM) will be administered on Day 1 and Day 15 of Cycle 1 and only Day 1 of any subsequent 28-day cycle.
- l) Physical examination, performance status, vital signs and weight at baseline, weekly (D1, D8, D15, D22) during Cycle 1, twice during cycle 2 (D1 and D15), and then at the start of every cycle thereafter (within 3 days prior to treatment), or more frequently if clinically indicated. Finally at EOT/Progression.
- m) On copanlisib infusion days, blood pressure should be measured pre-dose, mid-infusion, end of infusion, and 1 and 2 hours after the end of infusion. Note: a window of ± 10 minutes is allowed for all BP measurements, except for pre-dose (0 hour) measurement
- n) MUGA scan or ECHO will be performed at screening and as clinically indicated. The same method should be used throughout the study.
- o) Hematology (CBC with platelet and differential WBC count) will be performed at baseline, weekly (D1, D8, D15, D22) during Cycle 1, twice during cycle 2 (D1 and D15), and then at the start of every cycle thereafter (within 3 days prior to treatment), or more frequently if clinically indicated. Finally at EOT/progression.
- p) Clinical chemistry (total protein, albumin, indirect and TB, AST, ALT, ALP, electrolytes [sodium, potassium, calcium, and magnesium], serum phosphate, serum creatinine, creatinine clearance, uric acid, and bile salts) will be performed at baseline, weekly (D1, D8, D15, D22) during Cycle 1, twice during cycle 2 (D1 and D15), and then at the start of every cycle thereafter (within 3 days prior to treatment), or more frequently if clinically indicated. Finally at EOT/progression.
- q) Mandatory blood samples to isolate plasma ctDNA will be collected at pre-treatment (Day -28 to Day 1 of Cycle 1), on-treatment (pre-dose on the same day as the on treatment biopsy on Cycle 2 Day 1, as well as during the first two restaging visits), and post-treatment at EoT. A maximum of 5 ctDNA samples will be collected per patient.
- r) Tumor biopsies, if medically feasible, will be obtained at Screening (within 28 days of Cycle 1 Day 1), on-treatment after fulvestrant and copanlisib administration on Cycle 2 Day 1 and at EOT. Tumor biopsies will be optional but encouraged, especially in patients with a response or prolonged disease control. Tumor biopsies will be used to evaluate genomic biomarkers of response and intrinsic and adaptive resistance, and to evaluate pharmacodynamic markers of engagement.
- s) Pregnancy tests will be only for women with childbearing potential. Only whole blood will be collected for the pregnancy test that will be performed in the Screening period (Day -28 to Day -1).
- t) Additional pregnancy tests will be performed at Day 1 of each Cycle only for women with childbearing potential. Whole blood or urine can be collected for the test.
- u) Pregnancy test for Cycle 1 Day 1 can be skipped if the test for the screening period is performed close to the 1st cycle.

- v) FPG testing will be performed at Screening and before each copanlisib administration on Day 1, Day 8, and Day 15 of each Cycle from Cycle 1 to Cycle 4 inclusive. Starting with Cycle 5, FPG testing will only be performed on Day 1 of each cycle.
- w) Patients who experience confirmed disease progression or initiate a new anticancer therapy will move into the survival follow-up phase. Patients will be contacted by telephone every 12 weeks (± 14 days) for survival status until death, withdrawal of consent, or lost to follow-up.

Proprietary Information of MD Anderson

Protocol 2020-1241

19 October 2022

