- **The following event is classified as a DLT:**

- If a full cycle of copanlisib (3 doses) will not be completed due to any study intervention-related AE, the AE is considered as a DLT
- A delay of over 1 week in initiating Cycle 2 of copanlisib and/or fulvestrant treatment occurs secondary to any study drug related AE, the AE will be considered a DLT
- Death not clearly attributed to underlying disease or alternative cause

Note: Allergic reactions leading to discontinuation of study interventions will not be considered as a DLT and participant will be replaced.

3.3 Exploratory endpoints:

Biomarker-based studies will be performed using tumor tissue and liquid biopsies to assess clonal evolution, and mechanisms of innate and adaptive resistance.

Tumor biopsies, if medically feasible, will be obtained at screening (within 28 days of Cycle 1, Day 1) on-treatment after fulvestrant and copanlisib administration on Cycle 2 Day 1 and at EOT. Biopsies will be optional but encouraged, especially in patients with a response or prolonged disease control. Examples of studies include identification of genomic biomarkers of response and intrinsic or adaptive resistance by whole exome, targeted NGS, and Nanostring DSP or other similar methods.

Proprietary Information of MD Anderson

Protocol 2020-1241

19 October 2022

[figure not shown]
Mandatory blood samples to isolate plasma ctDNA will be collected at pre-treatment (Day -28 to Day1 of Cycle 1), on-treatment (pre-dose -at the same time as the on treatment biopsy- on Cycle 2 Day 1 as well as at the first two restaging visits), and post-treatment at EoT.

Plasma ctDNA samples will be used to evaluate changes in ctDNA quantity and clonal evolution by selected molecular methods that may include targeted NGS, methylation sequencing, and droplet digital polymerase chain reaction.

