4.1.4 Follow-Up Visits

Patients who discontinue study treatment for a reason other than disease progression will move into the follow-up phase. Patients will be monitored for disease status by tumor imaging (CT scan or MRI, as appropriate) every 8 weeks (± 7 days) until PD, death, initiation of new anticancer therapy, withdrawal of consent, or lost to follow-up.

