6.2 Dose Modification

Any toxicity observed during the study can be managed by interruption of the dose of study treatments or dose reductions. Repeated dose interruptions are allowed as required, for a maximum of 4 weeks on each occasion. Where toxicity recurs following re-challenge with study drugs, and where further dose interruption is considered inadequate for toxicity management, then withdrawal is indicated.

[figure not shown]
If either of the study drugs or both drugs need to be held due to AEs, then the study drug deemed to be responsible for the AE will be held until AE resolves to grade 1 or baseline. When copanlisib or fulvestrant dosing is interrupted, either the patient must recover completely, or the toxicity must revert to NCI CTCAE \leq Grade 1 or baseline before restarting study treatment. Patients whose NCI CTCAE Grade 3 or 4 event does not resolve to \leq 1Grade or baseline within 4 weeks should be withdrawn from the study. When a patient withdraws prior to study completion, all applicable activities scheduled for the final study visit should be performed at the time of withdrawal. Any AEs that are present at the time of withdrawal should be followed until \leq Grade 1 or baseline.

Proprietary Information of MD Anderson

Protocol 2020-1241

19 October 2022

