6.3.1 Copanlisib toxicity management

Table 5: Management of Nausea/vomiting

Toxicity	Action to be Taken
CTCAE Grade 1	No change in dose
CTCAE Grade 2	Hold* until \leq Grade 1. No change in dose
CTCAE Grade 3	Hold* until \leq Grade 2. Resume at one dose level lower, if indicated.**
CTCAE Grade 4	Off copanlisib treatment

*Patients requiring a delay of >2 weeks may go off protocol therapy.
**Patients requiring >2 dose reductions should go off protocol therapy.

Recommended management: Antiemetics

Table 6: Management of Diarrhea

Toxicity	Action to be Taken
CTCAE Grade 1	No change in dose
CTCAE Grade 2	Hold* until \leq Grade 1. No change in dose
CTCAE Grade 3	Hold* until \leq Grade 2. Resume at one dose level lower, if indicated.**
CTCAE Grade 4	Off copanlisib treatment

*Patients requiring a delay of >2 weeks may go off protocol therapy.
**Patients requiring >2 dose reductions should go off protocol therapy.

Proprietary Information of MD Anderson

Protocol 2020-1241

19 October 2022

Recommended management: Loperamide antidiarrheal therapy

Dosage schedule: 4 mg at the first onset, followed by 2 mg with each loose motion until diarrhea-free for 12 hours (maximum dosage: 16 mg/24 hours)

Adjunct anti-diarrheal therapy is permitted and should be recorded when used.

Table 7: Management of thrombocytopenia

Toxicity	Action to be Taken
CTCAE Grade 1	No change in dose
CTCAE Grade 2	No change in dose
CTCAE Grade 3	Hold* until \leq Grade 1. Resume at one dose level lower, if indicated. **
CTCAE Grade 4	Off copanlisib treatment

*Patients requiring a delay of >2 weeks may go off protocol therapy.

**Patients requiring >2 dose reductions should go off protocol therapy.

Table 8: Management of Neutropenia

Toxicity	Action to be Taken
CTCAE Grade 1	No change in dose
CTCAE Grade 2	No change in dose
CTCAE Grade 3	Hold* until \leq Grade 2. Resume at one dose level lower, if indicated. **
CTCAE Grade 4	Off copanlisib treatment

*Patients requiring a delay of >2 weeks may go off protocol therapy.

**Patients requiring >2 dose reductions should go off protocol therapy.

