6.9 Patient Withdrawal/Discontinuation Criteria

Patients may withdraw consent at any time for any reason or be dropped from the study at the discretion of the investigator should any untoward effect occur. In addition, a patient may be withdrawn by the investigator if enrollment into the study is inappropriate, the study plan is violated, or for administrative and/or other safety reasons.

A patient must be discontinued from the study for any of the following reasons:

- The patient or legal representative withdraws consent. Every effort will be made to determine why any subject withdraws from the study prematurely.

A patient must be discontinued from study treatment (but may continue to be monitored in the study) for any of the following reasons:

- The patient or legal representative withdraws consent
- Confirmed radiographic disease progression with the exception of patients who are benefitting from the study treatment in the opinion of the investigator, the patient is clinically asymptomatic, and continuation of study treatment is approved by the sponsor.
- Unacceptable toxicity
- An intercurrent illness that prevents further administration of study treatment
- Investigator's decision to withdraw the patient
- The patient has a confirmed positive serum or urine pregnancy test
- Non-compliance with study treatment or procedure requirements
- Initiation of new anticancer therapy including another investigational agent
- The patient is lost to follow-up. A genuine effort must be made to determine the reason(s) why a patient fails to return for the necessary visits. If the subject is unreachable by telephone, a registered letter, at the minimum, should be sent requesting him/her to contact the clinic
- Death
- Dose interruption that exceeds 4 weeks
- Administrative reasons

When a patient is permanently discontinued from receiving study treatment prior to study completion, all applicable activities scheduled for the final study visit should be performed at the time of withdrawal. The patient will continue to be followed for safety unless consent is withdrawn or the patient is lost to follow-up or initiation of a new anticancer therapy. Patients who discontinue for reasons other than disease progression will have post-treatment follow-up for disease status until PD, death, initiation of new anticancer therapy, withdrawal of consent,

Proprietary Information of MD Anderson

Protocol 2020-1241

19 October 2022

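### On-treatment scans follow cycle Day 1, so a delay that moves Day 1 also postpones the scan and raises mean recorded PFS, modestly at plausible delay rates

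*Combined protocol and SAP*

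**What the plan says.** Footnote h of the Schedule of Assessments (Appendix A) sets imaging at screening, on Day 1 of Cycle 3, and then on Day 1 "of every 2nd cycle after that, and at EOT", with a 7-day window either side of each Day 1. Footnote j gives the cycle length: copanlisib is "administered on Day 1, Day 8, and Day 15 of 28-day cycles". Two undelayed cycles are therefore 8 weeks.

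Section 6.2 deals with holds: "Repeated dose interruptions are allowed as required, for a maximum of 4 weeks on each occasion". Section 6.9 requires discontinuation of treatment for "Dose interruption that exceeds 4 weeks". The notes to the toxicity tables in 6.3.1 are permissive: "Patients requiring a delay of >2 weeks may go off protocol therapy".

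The protocol foresees that toxicity can move a cycle start. One DLT criterion in section 3 applies when "A delay of over 1 week in initiating Cycle 2 of copanlisib and/or fulvestrant treatment occurs" because of a drug-related event. Section 6.3.4 also delays treatment by at least 14 days for active SARS-CoV-2 infection.

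For patients who stop treatment without progression, section 4.1.4 uses the calendar: "Patients will be monitored for disease status by tumor imaging (CT scan or MRI, as appropriate) every 8 weeks", with a 7-day window. Section 3.1 measures PFS from the start of treatment to progression or death. Section 2 lists it as secondary, and section 8.2 summarises secondary efficacy endpoints within cohorts.

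**The concern.** PFS runs in calendar time, but progression can only be recorded when a patient is scanned, and on treatment the scan date depends on how the cycles have gone. If a delay moves Day 1, the scan moves with it. The ±7-day window does not absorb this, because it is attached to the delayed Day 1. Two patients with the same tumour course can then have different recorded progression and first-response dates because one had a delayed cycle. Once a patient is off treatment the dependence disappears.

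The error is systematic and linked to tolerability, so a larger sample would not remove it. It enters the absolute PFS estimate for each cohort, which is the quantity a reader would set beside outside data. The readable text gives no PFS rule for late or missed scans that would limit it.

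**Working it through.** The plan states no figure on this point to reproduce: the readable text gives no assumed PFS and no expected rate of delays.

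**Scan interval.** Interval = 2 × 28 days + time by which Day 1 is moved.
- No delay: 56 days = 8 weeks.
- One 2-week delay: 10 weeks. One in each of the two cycles: 12 weeks.
- One 4-week delay: 12 weeks. One in each of the two cycles: 16 weeks.

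**Effect on mean recorded PFS.** Inputs from the protocol are the 8-week undelayed interval and the 4-week maximum hold. Assumed inputs are:
- exponential progression times with a true median *m* of 12 to 24 weeks;
- each cycle start delayed by *h* weeks with probability *p*, independently;
- progression recorded at the next scan.

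Let λ = ln 2 / *m* and let G be the interval between scans: 8 weeks with probability (1−*p*)², 8+*h* with probability 2*p*(1−*p*), and 8+2*h* with probability *p*². Then

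mean recorded PFS = E[G] / (1 − E[exp(−λG)]).

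With *m* = 12:
- Calendar scans: 8 / (1 − 0.6300) = 21.62 weeks.
- *p* = 10%, *h* = 2: E[G] = 0.81×8 + 0.18×10 + 0.01×12 = 8.4. E[exp(−λG)] = 0.81×0.6300 + 0.18×0.5612 + 0.01×0.5 = 0.6163. Mean = 8.4 / 0.3837 = 21.89, a shift of +0.27.
- *p* = 10%, *h* = 4: E[G] = 8.8, E[exp(−λG)] = 0.6042. Mean = 8.8 / 0.3958 = 22.24, a shift of +0.62.
- *p* = 50%, *h* = 4: E[G] = 12. E[exp(−λG)] = 0.25×0.6300 + 0.5×0.5 + 0.25×0.3969 = 0.5067. Mean = 12 / 0.4933 = 24.33, a shift of +2.71.

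The same formula over *m* = 12 to 24 weeks gives:

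| Cycles delayed | Length of delay | Shift in mean recorded PFS |
|---|---|---|
| 10% | 2 weeks | about +0.3 weeks |
| 10% | 4 weeks | about +0.6 weeks |
| 20% | 2 weeks | about +0.5 weeks |
| 30% | 4 weeks | +1.6 to +1.7 weeks |
| 50% | 4 weeks | +2.5 to +2.7 weeks |

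A simulation of 400,000 patients per setting agrees with these figures.

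**What the mean hides.** In the simulations behind the last three rows, 13% to 22% of patients were recorded as progressing earlier than on the calendar schedule, because a shifted scan can fall sooner after their progression. The median need not follow the mean. Take a true median of 18 weeks. Calendar scans at 8, 16 and 24 weeks record it at 24. One 2-week delay in every interval puts scans at 10 and 20, and the recorded median falls to 20. One 4-week delay in every interval puts scans at 12 and 24, and it stays at 24.

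**The case against.** The strongest reply is that many holds never move Day 1. Section 6.2 holds the drug judged responsible, which may be only one of the two. Fulvestrant is due on Day 1 of each cycle, so a copanlisib-only hold can leave the cycle clock running. Section 6.3.1.3 allows an interrupted infusion to be skipped. A reader might infer from section 6.2 that every permitted hold delays a scan. The documents do not support that, and the readable text does not say how cycles are counted during a hold. What stands is that some delays do move treatment as a whole: the delayed Cycle 2 start in the DLT criteria, holds of both agents under 6.3.3, and the SARS-CoV-2 delay.

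Second, the larger shifts need 30% to 50% of cycles delayed by the longest hold permitted. Nothing in the documents suggests such rates. At 10% of cycles, the shift is smaller than the ±7-day scan window. The model also treats every event as scan-detected and leaves out the EOT scan. Deaths are dated exactly, so both simplifications tend to overstate the effect. This is a fair limit on size. It does not change the direction of the mean.

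Third, PFS is secondary and the readable design has no control arm, so no between-arm contrast is biased. A reader might also infer a bias in ORR, the Part 2 primary endpoint. The same anchor dates the first response scan, but ORR depends on whether a response occurs, and no size for an ORR effect has been shown.

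Finally, parts of sections 4.1, 4.1.2, 6 and 8 are not readable, so a calendar rule there cannot be excluded. It would still conflict with footnote h as written.

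**Conclusion.** The point holds in a limited form. Footnote h lets a delay that moves Day 1 postpone the next scan, by up to 4 weeks per delay, while off-treatment imaging keeps to the calendar. Mean recorded PFS rises as a result: by about 0.3 to 0.6 weeks if 10% of cycles are delayed 2 to 4 weeks, and by about 2.7 weeks at the extreme. These sizes rest on assumed delay rates, an assumed true median of 12 to 24 weeks and exponential progression; none of these comes from the documents.

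It would go too far to say that toxicity lengthens PFS for each affected patient, or that the reported median PFS will be too long. Some patients are recorded earlier, and the median can stay put or fall. This is an inexpensive improvement to a secondary endpoint and does not threaten the trial's main conclusion.

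**What to change.** Reword footnote h so that tumour assessments take place every 8 weeks (±7 days) from Cycle 1 Day 1 by calendar, regardless of dose delays, until progression. This gives imaging the same starting point as PFS and the interval already used in 4.1.4. The drift caused by delays is then zero by construction. Reconcile the wording with any imaging schedule in the sections that are not readable here. No dosing or treatment rule needs to change.

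The cost is small but goes beyond wording:
- Some scans will not coincide with a dosing visit.
- Patients with delayed cycles will have more scans per cycle. Without delays the frequency is unchanged.
- Footnote q ties two ctDNA samples to the first two restaging visits. Check that the new timing still suits their purpose.
- Part 2 evaluability (section 5, just before 5.3) needs two completed cycles and one efficacy assessment. A week-8 scan during a delay could come before the second cycle is complete, so the rule should say whether that scan counts.
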